#### Abbreviated Title: Pomalidomide for cGvHD Version Date: 4/29/2025

had dose-limiting myelosuppression. Overall, 7 subjects had an anemia response and 2 a spleen response.

In another trial of pomalidomide in MPN-associated myelofibrosis, low-dose pomalidomide (0.5 mg/day) was given to 58 persons. Anemia response was documented only in persons with JAK2V617F (24 vs 0%; P=0.03). Nine of the 10 anemia responders became red blood cell–transfusion independent. Fourteen of 24 persons with platelets  $\leq 100 \times 10e9$  /L had a greater than 50% increase in platelets. Grade 3 or 4 thrombocytopenia/neutropenia occurred rarely. This study established low-dose pomalidomide as effective and safe in MPN-associated myelofibrosis with anemia.

#### 1.3.3.1 Pomalidomide in cGvHD

Pusic et al. reported results of a phase 2 study of pomalidomide in patients with cGvHD not controlled by corticosteroids. Eight subjects received 3 mg/day with dose reductions to 2 mg, 1 mg and 0.5 mg. Seven subjects required dose reduction because of muscle cramps, tremor and fatigue. Five subjects discontinued therapy for worsening of cGvHD of the skin and mouth (N=1), pain (N=1) and no response (N=3). No bone marrow suppression, somnolence, constipation or DVT were observed. Three persons reached the primary evaluation endpoint at 6 months at the 2 mg dose (N=2) or 1 mg dose (N=1). The 3 patients had global PRs per NIH criteria (skin erythema, GI) and <PR ongoing improvements in the skin, mouth and eyes. This study established feasibility of giving pomalidomide to humans with cGvHD and the absence of serious side effects at doses less than 2 mg/day.

Table 2.	Clinical	Studies	of Pon	nalidomide
----------	----------	---------	--------	------------

Reference	Setting	Study Design	Study Duration	Dose	N	MTD	Toxicities	Response Rate
Phase 1								
Celgene, not published	Healthy volunteers	Single-blind, placebo- controlled, ascending single dose		1, 5, 10, 25, 50 mg	30, 10 received placebo	N/A	Mild or moderate AEs; no clinically significant changes in any laboratory parameter tested	N/A
Streetly et al.,2008 	Relapsed MM	Standard dose escalation	4 weeks	1, 2, 5, 10 mg	20	5 mg	10 mg, grade 4 neutropenia in 3/3 pts, DVT 0%	10% CR and >50% reduction in paraprotein in 50%
Schey et al., 2004 	Relapsed or refractory MM	Dose escalating regimen	4 weeks	1, 2, 5, 10 mg	24	2 mg	Grade 3/4 neutropenia in 58% pts and DVT in 16%	17% CR, >25% reduction in paraprotein in 67%, >50% reduction in paraprotein in 54%
Phase 2								· • •
Tefferi et al. 2009 	Anemia associated with myelofibrosis	Randomized, double- blind, multicenter	Up to 12 28-day treatment cycles	4 arms (2 mg+ placebo, 2 mg + prednisone, 0.5 mg + prednisone, and prednisone + placebo	84	2 mg	Relatively low incidence of grade ≥3 neutropenia and thrombo-cytopenia	Response in anemia 20 pts (40%) 23%, 2 mg/d + placebo; 16%, 2 mg/d + prednisone; 36%, 0.5 mg/d + prednisone; 19%, prednisone + placebo

		D1 1/0	0.0.1		10			
Mesa et	Myelofibrosis	Phase $1/2$ ,	28 days	2.5, 3.0 and	19	3 mg	DLT myelosuppre-	7 pts anemia
al., 2009 68		multicenter		3.5  mg/day;			ssion in $2/3$ pts in	response, 2 spleen
		dose		no efficacy			3.5 mg cohort	response
		escalation		at 3 mg,				
				dose				
				reduction to				
				0.5 mg				
Lacy et al.,	Relapsed	Multicenter	2 mg/d	2mg/day	60		Primarily	Objective response
2009 69	MM		on days				myelosuppression.	in 63%, including
			1-28 of a				Grade 3 or 4	CR in 5%, very
			28-day				hemato-logic	good PR in 28%
			cycle,				toxicity consisted	and PR in 30%
			dexame-				of anemia (5%),	
			thasone				thrombo-cytopenia	
			40 mg				(3%) and	
			on davs				neutropenia (32%)	
			1. 8. 15.				1 (- )	
			22					
Begna et	Myelofibrosis	Single-	28-day	0.5  mg/day,	58	2 mg	No AE reason for	10 (17%) anemia
al., 2011 	(JAK2V617F	center	cycles:	after 6			stopping therapy. 1	response, 20%
	positive)		84% pts	cycles			pt neuropathy, 1 pt	anemia RR in pts
			had $\geq 3$	2 mg/day			grade3/4 thrombo-	who received $\geq 3$
			cycles				cytopenia	cycles
Pusic et	cGvHD	Multicenter,		3 mg/day	8	3 mg	Muscle cramps,	2 CRs, 1 PR
al., 2010 		response		with dose			tremor and fatigue	(3 pts reached
		evaluated		reductions				6 months)
		every 3		to 2, 1 and				
		months		0.5  mg/dav				

#### 1.4 STUDY DESIGN AND RATIONALE

Better therapies for cGvHD are needed. In about 50% of persons with cGvHD, the disease does not respond to corticosteroids, and there is no standard second-line therapy or FDA-approved drug for cGvHD. Thalidomide is an immune-modulating drug effective in a rodent model of cGvHD and in humans for salvage therapy after failure of steroids, but at doses expected to be effective it is associated with troublesome side effects including somnolence, neuropathy and constipation, which precluded wider use in this population. Pomalidomide is a new immune-modulating drug that is more potent than thalidomide and has been shown in early trials in cancer and cGvHD to be without the toxicities that limited the use of thalidomide. Several biological features of pomalidomide suggest that this drug may be useful in treating cGvHD. Since the precise pathogenesis of cGvHD is unknown, the most compelling evidence for testing pomalidomide in a clinical trial is the encouraging efficacy data with thalidomide. Preliminary studies of pomalidomide in persons with cGvHD suggest absence of typical thalidomide-related side effects or significant myelosuppression and a preliminary suggestion of efficacy if doses of less than 3 mg/day could be given for at least 6 months (the typical primary response evaluation time point in cGvHD trials).

The use of the NIH Consensus Diagnosis, Staging Criteria now provides an updated, standardized assessment of persons with cGvHD for inclusion in clinical trials. Although NIH Consensus Response Criteria are not yet validated in large clinical trials there are preliminary data on validity and reproducibility that provide guidance for further use and testing.

At the intramural NCI there is a well-established clinical research infrastructure, the "NIH Chronic GVHD Study Group," that is uniquely qualified to conduct drug development studies and cGvHD assessments in a multi-disciplinary specialty setting. This environment is also uniquely conducive for further studies of cGvHD biology and in vivo pomalidomide effects by using the ETIB immunology pre-clinical core and the established cGvHD murine models expertise. The proposed study is not only expected to address a specific clinical therapeutic question related to pomalidomide in cGvHD but also allows establishment of experience with this important group of agents in general in patients after allogeneic hematopoietic stem cell transplantation.

The proposed study is a randomized phase 2 trial with the single stage selection design Patients will receive either a constant low dose of pomalidomide (0.5 mg/day) for six months or a strategy of increasing dose of pomalidomide from 0.5 mg/d up through each individual patients' maximum tolerated dose, with escalations by 0.5 mg/d every 2 weeks to a maximum of 2.0 mg/d. To protect patient safety, an early stopping rule will be implemented as outlined in section **8**. With two arms, each of which has a maximal accrual of 16 patients, up to 32 evaluable patients will be randomized. Response assessments will occur every 3 months with primary efficacy endpoint evaluated at 6 months. Patients with responding disease will continue therapy for another 6 months.

## 2 ELIGIBILITY ASSESSMENT AND ENROLLMENT

#### 2.1 ELIGIBILITY CRITERIA

#### 2.1.1 Inclusion Criteria

- 2.1.1.1 Moderate or severe cGvHD diagnosed and staged per NIH criteria (Filipovich et al 2005), Appendix C, Appendix D, Appendix E and Appendix F..
- 2.1.1.2 ≥18-75 years of age, because no dosing or adverse event data are currently available on the use of pomalidomide in persons <18 years of age
- 2.1.1.3 Has cGvHD that did not respond to high-dose corticosteroids (average 0.5 mg/kg/d prednisone for ≥8 weeks) or second-line systemic therapy
- 2.1.1.4 If taking systemic therapy for cGvHD at the time of enrollment, must be on a stable or tapering schedule in the preceding 4 weeks (extracorporeal photopheresis has to be stopped at least by 4 weeks before enrollment)
- 2.1.1.5 Karnofsky performance score  $\geq 60\%$  (Appendix A)
- 2.1.1.6 Life expectancy >3 months
- 2.1.1.7 Stable primary malignancy for previous 3 months
- 2.1.1.8 Agree to adhere to methods of contraception and other fertility control measures as prescribed by the protocol
  - Agents of this class are known to be teratogenic, women of child-bearing potential and men must agree to use effective forms of contraception (hormonal or barrier method of birth control; abstinence) prior to study entry and for the duration of study participation. Should a woman become pregnant or suspect she is pregnant while she or her partner is participating in this study, she should inform her treating physician immediately.
  - Female Subjects
    - Females of childbearing potential (FCBP)† must have a negative serum or urine pregnancy test with a sensitivity of at least 25 mIU/mL within 10 14 days prior to and again within 24 hours of starting pomalidomide and must either commit to continued abstinence from heterosexual intercourse or begin TWO acceptable methods of birth control, one highly effective method and one additional effective method AT THE SAME TIME, at least 28 days before she starts taking pomalidomide. FCBP must also agree to ongoing pregnancy testing. Men must agree to use a latex condom during sexual contact with a FCBP even if they have had a vasectomy. All patients must be counseled every 28 days about pregnancy precautions and risks of fetal exposure through the POMALYST REMSTM program. See Appendix M: Risks of Fetal Exposure, Pregnancy Testing Guidelines and Acceptable Birth Control Methods.
  - Male Subjects
    - Must agree to use a latex condom during sexual contact with females of childbearing potential while participating in the study and for at least 28 days

<sup>† A female of childbearing potential is a sexually mature woman who: 1) has not undergone a hysterectomy or bilateral oophorectomy; or 2) has not been naturally postmenopausal for at least 24 consecutive months (i.e., has had menses at any time in the preceding 24 consecutive months).

following discontinuation of study drug even if he has undergone a successful vasectomy

- Will be warned that sharing study drug is prohibited and will be counseled about pregnancy precautions and potential risks of fetal exposure
- Must agree to abstain from donating blood, semen, or sperm during study participation and for at least 28 days after discontinuation of study drug.
- Must agree that if a pregnancy or a positive pregnancy test does occur in a study subject or the partner of a male study subject during study participation, study drug must be immediately discontinued.
- Patients must agree to not share study drug with anyone during participation in the study.
- 2.1.1.9 Ability of subject to understand and the willingness to sign a written informed consent document.
- 2.1.1.10 All study participants must be registered into the mandatory POMALYST REMS™ program, and be willing and able to comply with the requirements of the POMALYST REMS™ program.

## 2.1.2 Exclusion Criteria

- 2.1.2.1 Acute GvHD, classic (<day 100) or late-onset (>day 100) Appendix D
- 2.1.2.2 Systemic immune suppression or systemic therapy for cGvHD started within preceding 4 weeks including extracorporeal photopheresis
- 2.1.2.3 Hypersensitivity to thalidomide, lenalidomide or pomalidomide
- 2.1.2.4 Any serious medical condition which places the subject at an unacceptable risk if he or she were to participate in the study or confounds the ability to interpret data from the study, including, but not limited to, symptomatic congestive heart failure, unstable angina pectoris, cardiac arrhythmia, or psychiatric illness/social situations that would limit compliance with study requirements.
- 2.1.2.5 Neutrophil <1.0x10^9/L, platelets <75x10^9/L, estimated creatinine clearance <50 mL/min/1.73m^2 (Cockroft-Gault formula) total bilirubin >3 mg/dL, transaminase >3xUNL
- 2.1.2.6 Uncontrolled infection
- 2.1.2.7 Active HIV-1, HBV and/or HCV infection
- 2.1.2.8 Uncontrolled arrhythmias or symptomatic heart disease or LVEF <45%
- 2.1.2.9 Other cancer except that for which the transplant was done <2 years before study entry, except non-melanoma skin cancer or carcinoma in situ of the uterine cervix or breast
- 2.1.2.10 Taking other investigational drugs
- 2.1.2.11 NIH lung score 3 (Appendix E)
- 2.1.2.12 Pregnant women are excluded from this study because pomalidomide has potential for teratogenic effects. Because there is an unknown but potential risk for adverse events in nursing infants secondary to treatment of the mother with pomalidomide, breastfeeding must be discontinued while the mother is taking study drug and for at least 28 days after discontinuation of study drug. These potential risks may also apply to other agents used in this study.

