## **3 STUDY IMPLEMENTATION**

#### 3.1 STUDY DESIGN

The study is a randomized phase 2 trial with the single stage selection design. It is known from prior trials that the maximum tolerated dose of pomalidomide is about 3 mg/d in persons with bone marrow disorders receiving prior therapies for cancer, in cGvHD doses <3mg/d have been well tolerated. This study will explore clinical toxicity of gradual escalation of pomalidomide doses <3 mg/d in subjects with cGvHD. Patients will receive either a constant low dose of pomalidomide (0.5 mg/day) for six months or a strategy of increasing dose of pomalidomide from 0.5 mg/d up through each individual patients' maximum tolerated dose, with escalations by 0.5 mg/d every 2 weeks to a maximum of 2.0 mg/d. In each of the two arms, the trial will use a single stage design.

As an early stopping rule for futility as outlined in section **8**, if after 7 patients have enrolled on either arm, 0 have responded, then no further patients will be accrued to that arm as soon as this can be determined. To protect patient safety, an early stopping rule will be implemented. With two arms, each of which has a maximal accrual of 16 patients, up to 32 evaluable patients will be randomized. Safety assessments and pregnancy testing for FCBP will be performed at scheduled intervals as described in the Study Calendar.

Response will be assessed every 3 months while taking pomalidomide following the criteria in Section 6.2. The primary efficacy endpoint will be evaluated at 6 months. Efficacy outcome is defined as clinical response (CR or PR) in subjects who enter the study with stable cGvHD or stable disease for  $\geq$ 3 mo for subjects with progressive cGvHD at study-entry. (Stability will be assessed by the clinician and by the clinical exam at the screening evaluation based on the clinician estimate of the disease trajectory during the 3 months pre-randomization). Subjects who meet the response criteria at 6 months will continue therapy for another 6 months. If in the subject's best interest, efforts will be made to provide access to study drug on compassionate basis beyond the 12-month study endpoint.

Patients who discontinue therapy for any reason will be followed for up to 24 months after starting pomalidomide as described in Section **6.1.3**.

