Concurrent topical and ancillary treatments for cGvHD are allowed per standards of care and will be recorded (see Section 4). Other systemic immune suppression must stay stable or be tapered (systemic immunosuppression taper should be attempted no earlier than after 4-6 weeks on study), throughout the treatment with pomalidomide (with up to 2 steroid pulses allowed for disease stabilization per Section 4.1).

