# 4.2 OTHER TREATMENTS FOR CGvHD

Patients who are taking concomitant systemic agents for control of cGvHD, such as calcineurin inhibitors (e.g., tacrolimus or cyclosporine) or other immunosuppressants (e.g., mycophenolate or sirolimus) must be on a stable dose in the preceding 4 weeks with an intent to stop if possible after corticosteroids are at stable or supplementation doses (maximum 7.5 mg prednisone/day) or discontinued. Patient should not receive any investigational drugs or initiate any systemic therapy for cGvHD once started on pomalidomide. Patient should not be undergoing extracorporeal photopheresis (ECP) concomitantly with study drug, and if they had ECP in the past, a minimum of 4 weeks should have passed since its discontinuation.

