#### 6.2.2.1 Response Criteria

Efficacy will be assessed using NIH consensus criteria measuring for therapeutic response in clinical trials for cGvHD:

- **CR** is defined as complete resolution in all of signs and symptoms at all affected organs or tissues.
- **PR** is defined as improvement in ≥ 1 organ or tissue with no progression in any other affected organ or tissue. The calculations for PR and progressive disease (PD) are provided in Appendix H and Appendix I.
- **Response** < **PR** is defined as change towards improvement from the pre-treatment baseline but not meeting the criteria for CR or PR.
- **Stable Disease** is defined as no change in cGvHD, SD will be considered as response in patients with documented cGvHD progression over preceding 3 months.
- **Flare** is defined as exacerbation of cGvHD manifestations during withdrawal of immunosuppressive therapy which do not exceed those at the beginning of the trial and improves after reinstatement of previous treatment.
- **Progressive disease** is defined as failure of therapy to control cGvHD. The calculations for progressive disease (PD) are provided in Appendix I. Assessment by Organ-Specific Criteria. Patients who progress prior to 6 months evaluation will be also evaluable for the primary efficacy endpoint.
- **Mixed response** (improvement in some organs but worsening in others) will be categorized as progressive disease.

As outlined in Section **3.5**, type of involved organ, location and its measurements will be recorded at scheduled evaluations and reported on the appropriate CRF, equal to "Chronic GVHD Assessment (Clinician) Form," (Appendix G). All other measurements not being included in primary assessment but clinically related to cGvHD (e.g., change of pigmentation) will be reported in the source documents.

Skin and skin appendages: Skin assessments include 4 anatomic level of skin involvement:

- (1) erythematous rash (epidermal),
- (2) movable sclerosis (dermal),
- (3) non-moveable sclerosis, hidebound skin, or involvement of subcutaneous tissue and fascia (subcutaneous) and
- (4) ulceration (full thickness loss of epidermal tissue).

The first 3 measurements should be taken separately and recorded in metric notation using a body surface area (BSA). A cutaneous assessment worksheet for recording the BSA is provided (Appendix J). The size of ulcer should be measured the longest diameter (LD) of the largest ulcer.

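### Entry trajectory is judged over 3 months but systemic cGvHD therapy need be settled for only 4 weeks, so stabilization by a recently started drug can be scored as a pomalidomide response

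*Combined protocol and SAP*

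**What the plan says.** Three provisions settle background therapy, all over four weeks. Section 2.1.2 excludes "Systemic immune suppression or systemic therapy for cGvHD started within preceding 4 weeks including extracorporeal photopheresis". Section 2.1.1 says that a patient already on systemic therapy "must be on a stable or tapering schedule in the preceding 4 weeks". Section 4.2 says that a patient on other systemic agents "must be on a stable dose in the preceding 4 weeks". These agents may go on during the study; section 3.1 adds that "Other systemic immune suppression must stay stable or be tapered".

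The endpoint looks back further. Section 3.1 requires CR or PR from patients who enter with stable cGvHD but accepts SD lasting at least 3 months from those who enter with progressive disease. The label is "based on the clinician estimate of the disease trajectory during the 3 months pre-randomization", together with the screening examination. Section 6.2.2.1 says that "SD will be considered as response in patients with documented cGvHD progression over preceding 3 months".

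Section 10 tests each arm of 16 against a fixed 5% response rate, with three or more responses as the bar.

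**The concern.** The look-back for trajectory is about three times as long as the period over which therapy must be settled. Take a patient who worsened until week −6, started a systemic agent at week −5 and has been steady since. The patient is eligible, may keep the agent on study, and on the literal wording of 6.2.2.1 has progressed within the preceding 3 months. Baseline may be taken within four weeks before study drug (section 2.6), so it can be recorded after the agent has begun to work. Holding that level at 6 months is then SD, and SD is enough.

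The stabilization may belong to the earlier drug. Both arms receive pomalidomide, so nothing inside the trial separates the two, and the 5% reference rate carries the whole inference. If such patients succeed more often than 5% without any pomalidomide effect, the test is no longer at its planned level.

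**Working it through.** **Is the gap closed elsewhere?** The requirement of non-response to corticosteroids or second-line therapy (2.1.1.3) can be met by an earlier steroid failure; it need not concern the newest drug. Sections 6.2.2, 6.2.2.1 and 10 contain no relabelling rule, exclusion or sensitivity analysis for patients whose therapy changed inside the 3-month window. The gap is open.

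**Width of the gap.** Three months is about 91 days and the exclusion covers 28. The open part is 91 − 28 = 63 days, or 63/91 = 69% of the trajectory window.

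**The plan's own figures.** Inputs from section 10: n = 16, null rate 5%, alternative 30%, success at three or more responses, one-sided level 0.10.

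- P(X ≥ 3 | 16, 0.05) = 1 − (0.4401 + 0.3706 + 0.1463) = 0.043.
- P(X ≥ 3 | 16, 0.30) = 0.901, which reproduces the stated 90% power.
- A cut-off of two would give P(X ≥ 2 | 16, 0.05) = 0.189, so three is the right cut-off for a level of 0.10.

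The attained 4.3% holds only if 5% is the null rate for the endpoint as scored.

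**Effect of affected patients.** Let k be the number per arm who are labelled progressive after being stabilized by a recent drug. Let q be their chance of scoring SD or better with no pomalidomide effect. Neither is in the documents; both are assumptions. The other 16 − k patients respond at 5%. Let X15 and X14 be binomial counts at 5% in 15 and 14 patients:

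- P(X15 ≥ 2) = 0.1710; P(X15 ≥ 3) = 0.0362.
- P(X14 ≥ 1) = 0.5123; P(X14 ≥ 2) = 0.1530; P(X14 ≥ 3) = 0.0301.

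For k = 1 the false-positive chance is q·P(X15 ≥ 2) + (1 − q)·P(X15 ≥ 3).

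- q = 0.3: 0.3 × 0.1710 + 0.7 × 0.0362 = 0.077
- q = 0.7: 0.7 × 0.1710 + 0.3 × 0.0362 = 0.131

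For k = 2 it is q²·P(X14 ≥ 1) + 2q(1 − q)·P(X14 ≥ 2) + (1 − q)²·P(X14 ≥ 3).

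- q = 0.3: 0.09 × 0.5123 + 0.42 × 0.1530 + 0.49 × 0.0301 = 0.125
- q = 0.7: 0.49 × 0.5123 + 0.42 × 0.1530 + 0.09 × 0.0301 = 0.318

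| Affected patients per arm | q = 0.3 | q = 0.5 | q = 0.7 |
|---|---|---|---|
| 0 | 4.3% | 4.3% | 4.3% |
| 1 | 7.7% | 10.4% | 13.1% |
| 2 | 12.5% | 21.2% | 31.8% |

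The nominal 10% is passed by one such patient at q = 0.5, or by two at q = 0.3.

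**The case against.** Several points on the other side stand.

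- **The label is not automatic.** A reader might infer that every such patient counts as progressive and scores as a success. Section 3.1 leaves the label to a "clinician estimate of the disease trajectory during the 3 months pre-randomization", and a clinician may call five steady weeks stable, in which case CR or PR is needed. The documents support *can count*, not *counts*.
- **SD has to last.** It must hold for at least 3 months, with evaluation at 6 months, and a mixed response is scored as progression (6.2.2.1).
- **Background therapy may fall.** Sections 3.1, 4.1 and 4.2 foresee tapering, so carried-over stabilization may have to survive decreasing immunosuppression. That argues for a lower q; it does not make q equal to 5%.
- **A larger effect can be computed, but it is not supported.** Suppose 10% to 30% of all patients had a recent change and 30% to 60% of those stabilize from it. If every one of them is labelled progressive, the false-positive chance is 13% to 72%. If only half are so labelled, it is 8% to 37%. The documents give none of these fractions, which is why the working counts labelled patients directly.
- **Eight weeks against four is not a contradiction.** The "average 0.5 mg/kg/d prednisone for ≥8 weeks" in 2.1.1.3 defines failure of corticosteroids; the four weeks define a settled background. They serve different purposes.
- **Other decisions are largely spared.** The futility look in section 10 counts only PR and CR, so these SD patients cannot rescue an arm there. Randomization should spread them over both arms, so selection gains noise more than bias.

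What remains is that no rule decides the label, and the literal wording of 6.2.2.1 favours the lower bar.

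**Conclusion.** The mismatch is real and nothing in the documents resolves it. Its consequence is possible rather than certain: a patient stabilized by an agent started or increased 4 to 13 weeks before randomization can be credited to pomalidomide by holding SD.

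The size depends on two unknowns, the number of such patients and their chance of SD from the earlier drug. It also assumes that the 5% null does not already allow for recent background therapy; section 10 does not say how 5% was chosen. Under the stated range, one patient per arm is enough to bring the false-positive chance near or above the nominal 10%, and two put it above 10% throughout. This is a threat to each arm's test against 5%, and it merits a cheap correction. It does not invalidate the design.

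**What to change.** In sections 3.1 and 6.2.2.1, add a rule for patients whose systemic cGvHD therapy was started or increased within 3 months before randomization: judge trajectory only over the time since that change. SD counts as response only if progression is documented after the change; otherwise CR or PR is needed. A patient still worsening on the recent drug therefore keeps the SD route, where stabilization is informative.

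Derive a flag for these patients. Prior and current treatments are already recorded at baseline (section 2.6), so the only check needed is that start and increase dates are captured. Prespecify a sensitivity analysis of the primary endpoint without the flagged patients. This also covers a PR carried over from the earlier drug, which the label rule alone does not reach. Fewer than 16 patients will remain per arm if any are flagged, so report this analysis with the 80% and 95% confidence limits that section 10 already plans, rather than by the 3-of-16 rule.

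The cost is one definition, one derived flag and one extra analysis. A few SD successes may be lost, so the observed response rate may be slightly lower. Eligibility and treatment rules are unchanged. If enrollment is already complete, the flag and the sensitivity analysis can still be added.
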